Stage 2: Patients who opt for DBS will be referred to the NHNN. At this visit the research protocol will be explained in detail to them. They will be offered the opportunity to visit the ward prior to admission. They will be seen in the multidisciplinary DBS clinic at the NHNN where they will be assessed for suitability for the surgery. Ability to provide written informed consent will be re-assessed at this stage thereby establishing consistency. Written informed consent will be taken at this stage if the patient is ready to decide. If the patient would like more time, written informed consent will be obtained at subsequent clinic appointments with [name] or [name].

Stage 3: Prior to surgery any serotonin reuptake inhibitor (SRI) medication will be withdrawn and they will remain free of this medication for the 10 days before surgery (see below). A time period of 7-21 days will be allowed for the careful down-titration of medication during the withdrawal process. The actual duration of withdrawal will be informed by decided by taking clinical and historical factors into account on a case-by-case basis. The participant might require an inpatient admission during the process of withdrawal from medication and a provision will be made for the same. We wish to undertake all assessments when patients are taking their routine medication. If they are taking SRIs we will undertake initial assessments at a separate visit to the hospital prior to admission for surgery and before their medication is withdrawn.

Stage 4: Patients will be admitted for DBS neurosurgery to a dedicated neuropsychiatry ward (Hughlings Jackson) at the NHNN. It is anticipated that they will stay for up to 14 nights, depending on whether the initial assessments have already been completed or not, and to allow post-operative recovery and the removal of the stitches by the surgical team 10 days after surgery.

Stage 5: Following discharge, stimulation will remain off for a minimum of 4 weeks to allow the mechanical effect of post-surgical oedema to resolve. This period can be extended, if necessitated by clinical reasons.

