6.1. Medication: Patients are likely to be taking a combination of high dose SRIs and antipsychotic medication. This medication will be kept constant throughout the study except for the preoperative period. Evidence suggests that patients taking SRIs are at increased risk of bleeding because of a non-dose dependent reduction in platelet serotonin²³. To decrease this risk, patients will be withdrawn from SRIs and be free of this medication for 10 days prior to surgery to allow platelets to be replaced. Medication will be reinstated during the post-operative period.

6.2. DBS Neurosurgery: All patients will undergo implantation of bilateral electrodes at both the VS/VC and STN sites under general anaesthesia. On each side, the two electrodes (STN and VC/VS) will be implanted through a single burr hole. A high-resolution MRI scan will be used to calculate target coordinates for each patient. An MRI will also be performed to verify accurate electrode location²⁴ immediately following surgery. Both scans will be performed under general anaesthesia. Each STN electrode will have 4 electrical contacts at its distal tip (with a 0.5mm separation) to allow fine tuning of the exact site for stimulation delivery. Each VS/VC electrode will have 4 electrical contacts at its distal tip (with a 1.5mm separation) to allow fine tuning of the exact site for stimulation delivery. Two non-rechargeable batteries (Activa PC) will be connected to the electrodes and positioned under the skin of the right and left chest wall so that they correspond to the same set of

electrodes for each patient: one for the 2 STN electrodes and one for the 2 VC/VS electrodes.

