6.7. TMS assessments

During TMS electromyography recordings will be made from abductor pollicis brevis (APB) and first dorsal interosseus (FDI) muscle using surface electrodes. Signals will be amplified and band pass filtered at a sample rate of 5000 Hz. TMS will be applied using a 70 mm figure of eight coil and Magstim 200 generators.

- a. **Cortical plasticity assessment:**
Paired associative stimulation (PAS) after localisation of the “hotspot” the resting (RMT) and active (AMT) motor thresholds will be determined. At 0.5, 15 and 30 min after PAS, we will obtain a stimulus response curve; MEPs will be recorded at each intensity from RMT-10% maximum stimulator output to RMT+30%. The inhibitory PAS10 paradigm (200 pairs, at 0.25 Hz) will be used. Median nerve stimulation (constant current generator) at 3x perceptual threshold intensity (duration 0.2 ms) will be delivered before TMS over the APB “hotspot” (intensity at 1 mV MEP prior to the start of the procedure).
- b. **Intracortical inhibition (SICI) assessment:**
TMS will be delivered to the FDI “hotspot”. The first, conditioning-stimulus, will be set at 80% AMT and the second, test stimulus at a 1 mV MEP level when given alone. Interstimulus intervals of ^{2,3} will be explored (n=12 per interval, randomly intermixed). SICI will be calculated by pooling 2 and 3 ms data and expressed as the ratio between conditioned and unconditioned trials. SICI will also be combined with a reward paradigm ²¹.

6.8. Timing of assessments and procedures: *(Please also see Table 1)* All assessment will be performed prior to surgery. Cognitive and TMS assessments will be performed additionally at the end of each of the 3 DBS periods, at the end of the optimisation of DBS period and at the end of CBT. Where possible, alternative forms of the tests will be used to avoid practice effects. Clinician-based clinical assessments will additionally take place monthly or more often if judged necessary. Patient self-report assessments will additionally take place at the end of each of the 3 DBS periods, at the end of the optimisation of DBS period and at the end of CBT.

7. Data Analysis

7.1. Descriptive analysis will be used to quantify changes in clinician-related YBOCS scores by using visual plots and specifying means and 95% CIs or medians and IQRs. We will then compare these changes using Friedman's ANOVA to account for the lack of independence between observations.

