7.2. The primary efficacy measure will be the clinician-rated YBOCS total scores. Friedman's ANOVA across all 4 conditions (pre-op baseline and after 3 months DBS in STN, VC/VS and STN+VC/VS) will be performed. A categorical efficacy measure, responder/non-responder status after each 3 month DBS block will be defined as $\geq 35\%$ decrease in YBOCS and will be analysed with the McNemar exact test for comparison of the VC/VS and STN DBS conditions. Descriptive analysis in addition to Friedman's ANOVA will also be used to analyse the mechanistic hypotheses on the following variables: MADRS, SSRT, ID/ED, probabilistic reversal learning, affective go/no go scores and TMS. The additional benefit of CBT will be analysed using Wilcoxon matched-pairs before and after CBT.

7.3. These data will also allow an estimate of mean effect and variance of the main effect to be made to allow a sample size calculation for a future fully powered trial.

8. Ethics and patient safety

8.1. Clinical care: All patients will be under the care of NHS OCD specialised services and their local community mental health team (CMHT). Consistent with the existing nationally commissioned clinical pathway, all potential participants will be offered the choice of anterior cingulotomy or DBS. Although this study is designed to examine the effect of DBS and not to compare the two procedures, adopting the standard care pathway will ensure that existing robust governance and consent procedures will be applied for all participants.

8.2. Monitoring for potential DBS adverse effects: The published risks of STN and VC/VS stimulation are mainly hypomania and anxiety, which are voltage dependent and 8, 9 and either self-limiting or resolved by modifying the stimulation settings. Clinical worsening, including lowering of mood has also been reported after stimulation is switched off. To

monitor and manage any adverse effects, the following procedures will be in place for each patient:

- a. Prior to surgery, in conjunction with the responsible OCD clinician [name] the study research clinician will contact the CMHT, speak to the responsible consultant and key worker about the study and provide regular progress reports.
- b. Patients will remain in hospital following changes in DBS for at least 24 hours following the final stimulation adjustment.

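### The only unstimulated score in the primary analysis is pre-operative, so any lasting effect of implantation is counted together with stimulation in the contrast with baseline and possibly in the responder rate

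*Protocol*

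**What the plan says.** Section 7.2 sets the outcome: "The primary efficacy measure will be the clinician-rated YBOCS total scores". The test on it reads: "Friedman's ANOVA across all 4 conditions (pre-op baseline and after 3 months DBS in STN, VC/VS and STN+VC/VS) will be performed". Three of the four conditions are stimulation-on, and the fourth precedes surgery. A second measure follows: "A categorical efficacy measure, responder/non-responder status after each 3 month DBS block will be defined as" a fall of 35% or more in YBOCS. The score from which the fall is counted is not named, and the pre-operative score is the only baseline that section 7 mentions. Section 7.3 carries an effect estimate forward to size a later trial, without saying whether it is a change from baseline or a difference between sites.

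Section 5.4 gives the order of events. Patients taking SRIs have their initial assessments before these are withdrawn (Stage 3). Surgery follows (Stage 4). In Stage 5 "stimulation will remain off for a minimum of 4 weeks to allow the mechanical effect of post-surgical oedema to resolve", and the period can be extended. On SRIs, section 6.1 says "Medication will be reinstated during the post-operative period", with no date. On ratings, section 6.8 says "Clinician-based clinical assessments will additionally take place monthly or more often if judged necessary". The text ties no rating to the end of Stage 5, and section 7 uses none from it.

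**The concern.** Between the pre-operative score and the first stimulation, four leads are implanted, patients know they have had surgery, and weeks pass. If YBOCS shifts over that interval and the shift lasts, every stimulated condition carries it and the reference does not. The four-condition test can then be significant, and a patient can be called a responder, for reasons other than stimulation. If the effect in section 7.3 means change from baseline, the later trial would be sized on the sum of implantation and stimulation. The Stage 1b group can speak to the passage of time but not to implantation, because it has no surgery. A score taken with leads in place and stimulation off would separate the two, and it cannot be recovered once Stage 6 begins.

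**Working it through.** The protocol gives no power or sample-size figure, so there is nothing of its own to reproduce.

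**Inputs from the protocol.** Six patients (4.1); minimum YBOCS at entry 32 (4.2); four conditions (7.2); response at a 35% fall (7.2); stimulation off for at least 4 weeks after discharge (5.4, Stage 5); up to 2 weeks of optimisation outside each 12-week block (5.4, Stage 6; 6.4).

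**Assumptions not in the protocol.** A constant implantation effect of 0 to 8 YBOCS points, and a within-patient SD of 3 or 5.

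**1. What the four-condition test can show.** With n = 6 and k = 4, Q = 12/(nk(k+1)) × ΣR² − 3n(k+1). Let every patient score worst before surgery and let the DBS conditions have equal rank sums: R = 24, 12, 12, 12.

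ΣR² = 576 + 3 × 144 = 1008. Q = 0.1 × 1008 − 90 = 10.8, and p = 0.013 on 3 degrees of freedom. The result is significant with no site difference and no need for a stimulation effect.

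**2. How often implantation alone would trigger it.** This was simulated with 100,000 trials per case, zero stimulation effect, and critical value Q ≥ 7.6 (actual level 4.3%).

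| Assumed lasting fall | SD 3 | SD 5 |
|---|---|---|
| 0 points | 4.3% | 4.3% |
| 2 points | 12% | 7% |
| 4 points | 40% | 16% |
| 6 points | 74% | 33% |
| 8 points | 93% | 54% |

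With a stimulation-off score that contains the whole shift as the fourth condition, rejection stays at about 4.3%. A Friedman test on the three DBS conditions alone (critical value 7.0) stays at about 2.9% throughout.

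**3. Responder rule, if the pre-operative score is the reference.** At baseline 32 the required fall is 0.35 × 32 = 11.2, to 20.8.
- Assumed prior fall of 4: 11.2 − 4 = 7.2 points remain, and 7.2/28 = 25.7% of the stimulation-off score.
- Assumed prior fall of 8: 11.2 − 8 = 3.2 points remain, and 3.2/24 = 13.3%.

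**4. Site comparison.** (STN − reference) − (VC/VS − reference) = STN − VC/VS. The reference cancels, so within-patient differences and ranks among DBS conditions do not depend on it. Responder status can change with the reference, but the same cut-off applies to both sites.

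**5. Would the Stage 5 score be a safe replacement?** Suppose YBOCS stands at 36 at the end of Stage 5 because SRIs have not yet taken hold again. Response against that score means 0.65 × 36 = 23.4 or less. If medication alone later returns the patient to 32, then 32 − 23.4 = 8.6 points (26.9% of 32) make a responder, against 11.2 under the pre-operative reference. Four points of drug recovery would be credited to DBS.

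**The case against.** The strongest reply is section 5.2(b): the study compares sites and does not seek absolute efficacy at each, which the protocol says would need on and off phases. For STN against VC/VS this reply stands. A constant implantation effect cancels. One that fades is a period effect, counterbalanced three to three between the two sites. The combined condition is always last and is not counterbalanced, but a Stage 5 score would not cure that. The reply does not cover section 7.2, which still puts the pre-surgical score into the primary test and defines response as a percentage fall.

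A reader might also infer that SRI withdrawal and restart are counted as response. The text does not support that. The baseline precedes withdrawal, medication is reinstated and otherwise held constant (6.1), and assessments are meant to be on routine medication (5.4, Stage 3). The first block ends at least 4 + 12 = 16 weeks after discharge, or 18 with full optimisation. What remains is an undated restart.

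Nor does the protocol show a large implantation effect. Section 5.3 reports that patients moved to sham returned to baseline severity within 2 or 4 weeks, which points against one, although that baseline is not defined. Finally, Table 1, to which section 6.8 refers, was not available for this check and may already place a rating in Stage 5.

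**Conclusion.** The point holds in a limited form. No implanted, stimulation-off score enters the analysis in section 7. The four-condition Friedman test therefore cannot tell stimulation from lasting effects of implantation, expectation or time, and a significant result need not reflect a difference between sites. The same mixture enters the responder rate if its reference is pre-operative, and the effect in section 7.3 if that is change from baseline; the protocol states neither. The direction follows from the design. The rejection rates and the 13% to 26% responder equivalents rest on assumed shifts and are illustrations only.

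It would be tempting to conclude that the Stage 5 score is the right reference and should replace the pre-operative one. It should not: it may fall only weeks after an undated SRI restart, while section 4.2 counts 12 weeks as the minimum for an SRI trial. This is a worthwhile, inexpensive improvement and not a defect in the comparison of STN with VC/VS.

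**What to change.** - **Section 6.8:** fix one of the planned monthly clinician ratings (YBOCS, MADRS, HAS) at the end of Stage 5, before any stimulation, and record the SRI restart date and medication status with it.
- **Section 7.2, reference:** keep the pre-operative score as the reference and say that the 35% rule refers to it. Report change and response against the Stage 5 score as an added stimulation-off reference.
- **Section 7.2, test:** test the three DBS conditions separately from the contrast with baseline.
- **Section 7.3:** say which effect is carried forward.

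The cost is protocol wording and one rating fixed in time at a contact already planned. Response rates against the added reference may look less favourable. The Stage 5 score needs caution where SRI effects may not have re-established, and it does not capture expectation that arises only once stimulation is switched on.

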6.7. TMS assessments

During TMS electromyography recordings will be made from abductor pollicis brevis (APB) and first dorsal interosseus (FDI) muscle using surface electrodes. Signals will be amplified and band pass filtered at a sample rate of 5000 Hz. TMS will be applied using a 70 mm figure of eight coil and Magstim 200 generators.

- a. **Cortical plasticity assessment:**
Paired associative stimulation (PAS) after localisation of the “hotspot” the resting (RMT) and active (AMT) motor thresholds will be determined. At 0.5, 15 and 30 min after PAS, we will obtain a stimulus response curve; MEPs will be recorded at each intensity from RMT-10% maximum stimulator output to RMT+30%. The inhibitory PAS10 paradigm (200 pairs, at 0.25 Hz) will be used. Median nerve stimulation (constant current generator) at 3x perceptual threshold intensity (duration 0.2 ms) will be delivered before TMS over the APB “hotspot” (intensity at 1 mV MEP prior to the start of the procedure).
- b. **Intracortical inhibition (SICI) assessment:**
TMS will be delivered to the FDI “hotspot”. The first, conditioning-stimulus, will be set at 80% AMT and the second, test stimulus at a 1 mV MEP level when given alone. Interstimulus intervals of ^{2,3} will be explored (n=12 per interval, randomly intermixed). SICI will be calculated by pooling 2 and 3 ms data and expressed as the ratio between conditioned and unconditioned trials. SICI will also be combined with a reward paradigm ²¹.

6.8. Timing of assessments and procedures: *(Please also see Table 1)* All assessment will be performed prior to surgery. Cognitive and TMS assessments will be performed additionally at the end of each of the 3 DBS periods, at the end of the optimisation of DBS period and at the end of CBT. Where possible, alternative forms of the tests will be used to avoid practice effects. Clinician-based clinical assessments will additionally take place monthly or more often if judged necessary. Patient self-report assessments will additionally take place at the end of each of the 3 DBS periods, at the end of the optimisation of DBS period and at the end of CBT.

7. Data Analysis

7.1. Descriptive analysis will be used to quantify changes in clinician-related YBOCS scores by using visual plots and specifying means and 95% CIs or medians and IQRs. We will then compare these changes using Friedman's ANOVA to account for the lack of independence between observations.

7.2. The primary efficacy measure will be the clinician-rated YBOCS total scores. Friedman's ANOVA across all 4 conditions (pre-op baseline and after 3 months DBS in STN, VC/VS and STN+VC/VS) will be performed. A categorical efficacy measure, responder/non-responder status after each 3 month DBS block will be defined as $\geq 35\%$ decrease in YBOCS and will be analysed with the McNemar exact test for comparison of the VC/VS and STN DBS conditions. Descriptive analysis in addition to Friedman's ANOVA will also be used to analyse the mechanistic hypotheses on the following variables: MADRS, SSRT, ID/ED, probabilistic reversal learning, affective go/no go scores and TMS. The additional benefit of CBT will be analysed using Wilcoxon matched-pairs before and after CBT.

7.3. These data will also allow an estimate of mean effect and variance of the main effect to be made to allow a sample size calculation for a future fully powered trial.

8. Ethics and patient safety

8.1. Clinical care: All patients will be under the care of NHS OCD specialised services and their local community mental health team (CMHT). Consistent with the existing nationally commissioned clinical pathway, all potential participants will be offered the choice of anterior cingulotomy or DBS. Although this study is designed to examine the effect of DBS and not to compare the two procedures, adopting the standard care pathway will ensure that existing robust governance and consent procedures will be applied for all participants.

8.2. Monitoring for potential DBS adverse effects: The published risks of STN and VC/VS stimulation are mainly hypomania and anxiety, which are voltage dependent and 8, 9 and either self-limiting or resolved by modifying the stimulation settings. Clinical worsening, including lowering of mood has also been reported after stimulation is switched off. To

monitor and manage any adverse effects, the following procedures will be in place for each patient:

- a. Prior to surgery, in conjunction with the responsible OCD clinician [name] the study research clinician will contact the CMHT, speak to the responsible consultant and key worker about the study and provide regular progress reports.
- b. Patients will remain in hospital following changes in DBS for at least 24 hours following the final stimulation adjustment.
- c. Following discharge and throughout the 12 month experimental period, when the optimal stimulation site(s) and parameters are being established, patients will be assessed for adverse effects and change in mental state by the study research clinician weekly.
- d. The study research clinician or deputy will be directly contactable by telephone in between these assessments 24/7.
- e. If adverse events arise or mental state worsens, they will be seen urgently by the study team and be readmitted to NHNN if necessary.
- f. The local mental health crisis team will be aware of the study and act as an emergency safety net for contact and assessment.
- g. Following the completion of the study all patients will be seen by the DBS team at least every 6 months for the rest of their lives unless DBS is permanently switched off.

8.3. Neurosurgery: In the last 9 years over 300 patients with movement disorders and chronic pain syndromes have undergone DBS in our unit at Queen Square, The senior surgeon [name] has over 23 years' experience with stereotactic neurosurgery in Sweden and the NHNN, including anterior capsulotomy for OCD and STN DBS for Parkinson's disease. The other surgeon has experience with more than 150 DBS procedures in several brain targets for many conditions including Parkinson's disease, dystonia, deafferentation pain, cluster headache, Tourette's syndrome and essential tremor. There have been no fatalities or clinically relevant haemorrhages. The safety and efficacy data emerging from the Unit of Functional Neurosurgery have been described as "a new benchmark" in functional neurosurgery ⁴². Implantation of 2 electrodes (one on each side) is standard. The technique used for electrode implantation is such that the added surgical risk by implanting 4 electrodes rather than two is negligible - some of the Unit's movement disorders patients have needed implantation of 4 electrodes, 2 in each hemisphere in different targets, without complications, for example in dystonia (pallidum and thalamus) and Parkinson's disease (pallidum and subthalamic nucleus). There are also many examples in the literature of patients undergoing double target electrode implantation and stimulation safely and with significant efficacy. Such double targets have included: pedunclopontine nucleus and STN; motor and limbic areas of internal pallidum; associative areas of both thalamus and internal pallidum ^{43, 44, 45, 46}.

9. Research team and environment

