- 1.3. Before DBS for OCD can be introduced into routine clinical practice, further research is required to determine the optimum DBS brain target. It may also be possible to improve upon the degree of response to DBS by understanding more about the mechanisms of action at the two target sites - although two-thirds were considered responders in previous studies, the patients remained symptomatic, being reduced from the 'extreme/severe' to the 'moderate' category ⁷. Furthermore, although CBT will not have previously been effective in these patients, DBS may reduce symptoms enough to enable them to use CBT more effectively and, indeed, the combination may result in a better outcome than DBS alone. To address these questions we have brought together a network of specialist OCD clinicians, leading OCD cognitive neuroscientists and expert DBS clinicians to undertake the first UK study of DBS for severe, medically intractable OCD.

2. Aims and Hypothesis

2.1. The overarching aim is to compare the effects of VC/VS and STN DBS in the same patients. We will test the hypothesis, grounded in cognitive neuroscience, that DBS at both sites is better than either site alone for treating the symptom dimensions of OCD. Specifically, we will employ novel cognitive paradigms and neurophysiological measures of cortical synaptic function to test the hypothesis that VS/VC and STN DBS have different mechanisms of action and that alleviation of OCD symptoms is mediated by improvement in mood/anxiety with VS/VC DBS and by directly interrupting obsessions and compulsions with STN DBS. We will additionally determine whether adjunctive CBT enhances the response to DBS by providing the cognitive and behavioural skills to optimise symptom management and daily function.

3. Scientific Rationale

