- 3.7.** OCD symptoms and cognitive impairment may be mediated by abnormal cortical excitability due to aberrant long term depression (LTD) synaptic plasticity¹⁸ and/or reduced GABA-mediated intracortical inhibition¹⁹. Transcranial magnetic stimulation (TMS) can be used to measure these neurophysiological processes safely in patients undergoing DBS and both abnormalities have been shown to normalise following DBS in other disorders²⁰. We will use TMS to assess these neural processes before and after DBS in OCD patients and test for whether there are differential changes from the two DBS sites and whether combined VS/VC and STN DBS produces more vigorous improvements compatible with our hypothesis concerning the superior clinical effects of this condition. We will measure intracortical inhibition not only at rest but also during the anticipation of reinforcement, previously shown to affect motor cortex excitability²¹ and which we predict will be specifically affected by VS/VC DBS.

4. Research Programme

- 4.1. Subjects:** Six patients will be recruited from the OCD National Specialist Commissioned Services of [name], South West London and St George's Mental Health Trust (SWLSG MHT) and [name], Herts Partnership NHS Foundation Trust (HPFT).
- 4.2. Inclusion criteria:** The inclusion criteria have been designed to be consistent with previous OCD DBS studies and to ensure that patients have not responded in a useful and sustained manner to either modifications of medication or any form of CBT⁴.

Patients must have undergone intensive treatment and have demonstrable treatment resistance as defined by:

- a. At least two SRIs for a minimum of 12 weeks at optimal British National Formulary (BNF) doses.
- b. Augmentation of SRI treatment with antipsychotic drugs administered at maximally tolerated doses or by extending the SSRI dose beyond BNF limits.
- c. Two trials of CBT of at least 10 hours.
- d. Failed inpatient treatment for OCD.

Patients must also satisfy the following criteria:

- e. Age > 20 years.

- f. Confirmation of a primary diagnosis of obsessive compulsive disorder (ICD10 F42.0—F42.9).
- g. Duration of illness of at least 10 years.
- h. At least 2 years of unremitting symptoms despite intensive psychopharmacological and psychological treatment or failure to sustain, over a 3 month period, a response to inpatient psychological treatment by at least 33% with accompanying optimised pharmacological therapy.

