4.3. Exclusion criteria

Current diagnoses of:

- a. Substance misuse (ICD10 F10—F19)
- b. Organic brain syndrome (ICD10 F00—F09)
- c. Adult personality disorder (ICD10 F60—F69)
- d. Pervasive developmental disorder (ICD10 F84)
- e. Schizophrenia (ICD10 F20-F29)
- f. Bipolar disorder (ICD 10 F30-31)
- g. Contraindications to neurosurgery
- h. Pregnancy

5. Study Design

See Figure 1

5.1. The study design will allow assessment of DBS at each of the two sites counterbalancing for order. Stimulation at both sites will not be included in the randomisation of order and will always occur last because:

- a. The optimal stimulation parameters for each target alone will have already been identified for each individual and thus the optimum parameters in combination will be determined more quickly; *and*
- b. We are predicting that stimulation of both sites will be the most efficacious condition and that withdrawal of effective therapy would risk higher rates of patient drop-out from the blinded evaluation and could be regarded as unethical.

5.2. We have opted not to have a wash-out period between the three DBS phases because:

- a. Patients may not wish to have the DBS switched off if they have experienced symptom reduction by the previous DBS settings and this will risk higher rates of

patient drop-out from the blinded evaluation; this has been experienced in one previous study⁸.

- b. The purpose of the study is to compare DBS at two sites both individually and together to establish the best site(s) for UK practice in the future - it is not to establish absolute efficacy at each site (which would require both on and off DBS phases) as this has been adequately demonstrated previously.

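### The primary Friedman test includes the pre-operative baseline, so it can be significant purely because YBOCS falls after surgery, even if the three DBS conditions do not differ

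*Protocol*

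**What the plan says.** Section 2.1 of the protocol gives the aim: "The overarching aim is to compare the effects of VC/VS and STN DBS in the same patients". Its clinical hypothesis is that "DBS at both sites is better than either site alone for treating the symptom dimensions of OCD". Section 5.2b, defending the lack of a wash-out, says the study is meant to find the best site or sites and that "it is not to establish absolute efficacy at each site".

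Section 7.2 then sets the analysis: "The primary efficacy measure will be the clinician-rated YBOCS total scores", tested by a Friedman "ANOVA across all 4 conditions (pre-op baseline and after 3 months DBS in STN, VC/VS and STN+VC/VS) will be performed". The same section adds one between-site test, an exact McNemar test of responder status (a fall of at least 35% in YBOCS) for VC/VS against STN. Section 7.1 plans plots with means and 95% CIs, or medians and IQRs. Section 4.1 sets the size of the DBS group at six. Section 5.1 fixes combined stimulation as the last DBS period for every patient.

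**The concern.** The null hypothesis of the four-condition test is that no condition differs from any other, baseline included. Patients enter with YBOCS of at least 32, and the background section quotes earlier response rates of 56%, 62% and 75%. A fall from baseline is therefore the largest difference to be expected among the four conditions, and it is also the comparison that section 5.2b sets aside.

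A significant primary result would be compatible with three identical DBS conditions, so it would not answer the question in section 2.1. This is more than detail left to a later document. The protocol itself names the set of conditions to be ranked, and that set does not fit its own aim.

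**Working it through.** The protocol gives no power, alpha or SD, so there is no stated figure to reproduce.

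**Inputs.** From the protocol: n = 6 (section 4.1); k = 4 conditions including baseline (section 7.2); minimum entry YBOCS 32 (section 4.2); response is a 35% fall (section 7.2), which at the entry minimum is 0.35 × 32 = 11.2 points. Assumed: alpha 0.05 and independent normal within-patient error with the SDs shown.

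**Step 1: baseline worst in every patient.** Q = 12/(nk(k+1)) × ΣR² − 3n(k+1). With n = 6 and k = 4 this is Q = 0.1 × ΣR² − 90. Rank 4 in all six patients gives baseline a rank sum of 24. All rank sums total 60, so the three DBS conditions share 36. ΣR² is smallest when they are equal, at 12 each:

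Q = 0.1 × (24² + 3 × 12²) − 90 = 0.1 × (576 + 432) − 90 = 10.8.

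Full enumeration of the null distribution gives exact p = 0.006; the chi-square approximation on 3 df gives p = 0.013. The exact 5% critical value is 7.6. Differences among the DBS conditions can only raise Q above 10.8, so the result is significant whatever the sites do.

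**Step 2: how far this extends.**
- Baseline worst in five patients and second worst in one (rank sum 23): minimum Q = 0.1 × (23² + 12² + 12² + 13²) − 90 = 8.6, exact p = 0.029.
- Baseline rank sum 22: minimum Q = 0.1 × (22² + 12² + 13² + 13²) − 90 = 6.6, exact p = 0.088. Significance is no longer assured.

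**Step 3: simulated rejection rates with three truly identical DBS conditions** (exact critical values).

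| Assumed drop from baseline | SD 3 | SD 5 | SD 7 |
|---|---|---|---|
| 12 points in every patient | 100% | 88% | 60% |
| 11.2 points in every patient | 99.6% | 83% | 54% |
| 4 points in every patient | 40% | 17% | 10% |
| 15 points in 60% of patients, 4 in the rest | 76% | 56% | 40% |
| 15 points in 60% of patients, none in the rest | 33% | 31% | 25% |

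A Friedman test on the three DBS conditions alone (exact critical value 7.0, attained alpha 0.029) rejects in about 3% of trials in every row.

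**Step 4: the other named test.** For the exact two-sided McNemar test, six discordant patients all in one direction give p = 2 × 0.5⁶ = 0.031. Five out of five give p = 2 × 0.5⁵ = 0.0625. It falls below 0.05 only if all six patients respond at one site and none at the other. It does not involve the combined condition.

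**Step 5: power of the three-condition test.** If each single site gives 11.2 points and both together give 16, power is about 25%, 17% and 12% at SD 4, 5 and 6. If both together give 20, it is about 70%, 50% and 37%.

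**The case against.** A reader might infer that the planned test turns significant whenever DBS helps at all. Step 3 does not support that: a small equal benefit usually leaves it non-significant, and a mixture of responders and non-responders, which the quoted response rates imply, lowers the rejection rate well below that for a uniform large drop.

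A reader might also infer that section 7.2 contains nothing on the choice of site. It does: the McNemar test addresses VC/VS against STN, and section 7.1 plans descriptive summaries. Pairwise follow-up comparisons may also sit in an analysis plan that is not shown, so their absence is not in itself a fault. What stands is that the protocol fixes the conditions of its primary test, and that its one named between-site test is nearly powerless at n = 6.

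It is tempting to see a contradiction between section 7.1, where "Descriptive analysis will be used to quantify changes in clinician-related YBOCS scores", and the four conditions of section 7.2, on the view that changes means three values per patient. That is only one reading. Changes can equally mean change across all conditions, so no contradiction is claimed.

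Finally, a corrected test does not settle the combined-site hypothesis. Combined stimulation always comes last (section 5.1), so any advantage over a single site is mixed with time. Requiring a Wilcoxon p below 0.05 against both single sites would need all six patients to favour the combination each time; for an assumed 4.8-point advantage that happens in about 24%, 6% and 2% of trials at SD 3, 5 and 7. This limits what the fix can achieve but does not justify the present test.

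**Conclusion.** The point holds in this form: the primary test can be significant solely because YBOCS falls from baseline, and that result would not bear on the aim in section 2.1 or the purpose in section 5.2b. Significance is certain if baseline ranks worst in all six patients, or worst in five and second worst in one. Those are rank results and need no assumption about drop or SD. How often a trial with identical DBS conditions would reject depends on the assumed drop, its spread between patients and the SD. It ranges from nearly always (uniform 12-point drop, SD 3) to about one trial in ten (uniform 4-point drop, SD 7). The hypothesis that both sites beat either alone has no named test in the protocol.

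**What to change.** In section 7.2:

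- Run the Friedman test on the three DBS conditions only, using the exact distribution for n = 6 and k = 3. Keep baseline against DBS as description.
- Report paired differences with 95% CIs for STN minus VC/VS, combined minus STN, and combined minus VC/VS.
- State that the two combined contrasts are confounded with time because combined stimulation always comes last (section 5.1).
- State that power is low with six patients, so these differences serve mainly as estimates for the future trial in section 7.3.

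The cost is rewording, with no new data. The downside is that a significant primary p-value becomes much less likely, because it would then require a difference between DBS conditions.
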